4.2.3.4 Asthma history

Asthma characteristics at baseline (age at asthma onset (Section 3.1.6.2), time since asthma diagnosis (Section 3.1.6.1), time since asthma symptoms started (Section 3.1.6.3), time since last asthma exacerbation (Section 3.1.6.4), total number of asthma exacerbations within previous 12 months prior to screening, including exacerbations resulted in non-emergency room treatment, emergency room treatment, hospitalization (Section 3.2.1.4)) will be summarised by treatment and overall for the ITT population. Descriptive summary statistics

will be produced for previous and concomitant treatments containing ICS and combination of products containing ICS. Asthma characteristics at baseline and previous and concomitant treatments containing ICS and combination of products containing ICS will also be listed for the ITT population.

4.2.3.5 Substance usage

Summary statistics will be produced by substance usage category (never, former, current), by treatment group and overall, for alcohol and tobacco use (as specified in Section 3.2.1.5) for the ITT population. Additionally, descriptive statistics on the number of pack-years for former or current cigarettes smokers will be provided.

4.2.3.6 Other assessments at Screening

Summary statistics for eDiary data at baseline such as 2-weekly mean PEF, 2-weekly mean FEV₁, number of days with awakening and rescue medication use, number of days with rescue medication used during the night and number of days with rescue medication use during the day, will be provided by treatment and overall.

4.2.4 Analysis of primary efficacy endpoint

4.2.4.1 Primary analysis of the primary endpoint

The primary efficacy endpoint is the change from baseline in pre-BD FEV₁ to Week 16.

The primary estimand is a 'Treatment Policy' estimand, as follows: The difference in mean change from baseline in pre-BD FEV₁ at Week 16 (MEDI3506 – placebo) will be analysed using MMRM (see Section 4.1.2) for the ITT population. This will include all available data from all visits up to and including Week 16, irrespective of whether the participant discontinued study intervention or received rescue therapy. Graphical representations of the LSMean change from baseline and the two-sided 80% CI over time will be provided by treatment group using the ITT population.

The observed values and change from baseline through Week 16 in pre-BD FEV₁ (L) by treatment group and visit will be summarised using the ITT population.

4.2.4.2 Supportive analysis of the primary endpoint

As a supportive analysis of the primary endpoint, the MMRM analysis (see Section 4.1.2) will be repeated on the ITT population using data from visits up to and including Week 16, but excluding the data from visits after IP discontinuation. Graphical representations of the LSMean change from baseline and the two-sided 80% CI over time will be provided by treatment group using the ITT population.

4.2.4.3 Subgroup analysis for the primary endpoint

For each of the subgroup factors (see Section 3.1.7) a separate MMRM will be fitted using the same covariates as described for the primary analysis in Section 4.2.4.1. Geographical region

will not be a covariate if it is the subgroup; baseline ICS total daily dose will not be a covariate if it is the subgroup; background medication will not be a covariate if it is the subgroup. MMRM results from subgroup analysis will be displayed using forest plot.

The observed values and change from baseline through Week 16 pre-BD FEV₁ (L) by treatment group, visit and subgroup will be summarised using the ITT population.

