To assess the longitudinal effect of MEDI3506 compared with placebo on lung function in adult participants with uncontrolled moderate-to-severe asthma.	As measured in clinic, change from baseline in pre-BD FEV1 to Weeks 1, 4, 8, 12, 20, and 24.
To assess the acute effect of MEDI3506 compared with placebo on pre-BD FEV1 in adult participants with uncontrolled moderate-to-severe asthma.	As measured in clinic, change in pre-BD FEV1 (L) from pre-administration of study intervention to 4 hours post-administration of MEDI3506 or placebo at Day 1.
To assess the effect of MEDI3506 compared with placebo on asthma control in adult participants with uncontrolled moderate-to-severe asthma.	During the intervention period (baseline to Week 16): 
 • Annualised rate of asthma exacerbations. • Annualised rate of hospitalised asthma exacerbations.
To assess the longitudinal effect of MEDI3506 compared with placebo on asthma control and health status in adult participants with uncontrolled moderate-to-severe asthma.	Change from baseline to Weeks 1, 4, 8, 12, and 24 in ACQ-6 score. Change from baseline to Weeks 4, 12, and 24 in SGRQ score. Change from baseline up to Week 24 in 2-weekly mean daily rescue medication usage (puffs/day). Change from baseline to Weeks 4, 8, 12, 16, 20, and 24 in: 
 • Asthma symptom score. • Mean number of night-time awakenings.
To assess the benefit-risk profile of MEDI3506 as perceived by adult participants with uncontrolled moderate-to-severe asthma.	PGI-BR at Week 16.
To evaluate CCI and inflammatory blood biomarkers that may predict an efficacy response to MEDI3506 in adult participants with uncontrolled moderate-to-severe asthma.	CCI  Association of allergen-specific IgE status with primary and secondary efficacy endpoints at Week 16.
To assess the effect of MEDI3506 compared with placebo on asthma related inflammatory airway biomarkers in adult participants with uncontrolled moderate-to-severe asthma.	Percent change from baseline to Weeks 1, 4, 8, 12, 16, 20, and 24 in concentration of FeNO. Change from baseline to Weeks 4, 8, 12, 16, 20, and 24 in exploratory biomarkers measured in nasal lining fluid. Change from baseline to Week 16 in mRNA nasal transcriptome.

Table 4 Objectives and Endpoints

Objective	Endpoint

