1.3 Number of participants

A sample size of 216 participants (72 participants per treatment group), randomised 1:1:1 to MEDI3506 **CC1** mg: MEDI3506 **CC1** mg: placebo, will provide at least 80% power to detect a statistically significant difference in change from baseline to Week 16 in pre-BD FEV₁, assuming a difference of 150 mL between placebo and MEDI3506, a between-participant SD of 420 mL and a one-sided- 10% alpha level. To allow for 5% participants being ineligible for the primary analysis, a total of approximately 228 participants will be randomised in the study (approximately 76/arm).

Up to 60 participants are intended to be included in the cough sub-study (approximately 20 participants per treatment group). However, given the exploratory nature of the sub-study and that it may not be activated in all countries, randomisation of participants not included in the sub-study will not be restricted, therefore, sub-study recruitment may not be achieved. Since limited data are available on cough monitoring in this population, the sub-study is considered exploratory and no formal power calculations have been performed.

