4.1.1 Statistical Hypotheses

The primary efficacy endpoint is the change from baseline in pre-BD FEV₁ at Week 16. A treatment policy estimand will be applied whereby all available data are included in the analysis, irrespective of whether a participant discontinued study intervention or received rescue therapy.

The null hypothesis is that the change from baseline in FEV₁ at Week 16 for participants dosed with MEDI3506 is equal to the change from baseline in FEV₁ at Week 16 for participants dosed with placebo. The alternative hypothesis is that the change from baseline in FEV₁ at Week 16 for participants dosed with MEDI3506 is greater than the change from baseline in FEV₁ at Week 16 for participants dosed with placebo, i.e.:

- H₀: Change from Baseline in FEV₁ at Week 16 (MEDI3506-placebo) = 0.
- H₁: Change from Baseline in FEV₁ at Week 16 (MEDI3506-placebo) > 0.

Hypothesis testing will be performed at the one-sided 10% level. If the p-value is < 0.1, reject H₀ and accept H₁. A hierarchical testing strategy will be used to preserve the type I error for the comparisons of each of the 2 dose levels of MEDI3506 versus placebo, as follows:

- Step 1: Test MEDI3506 **CC1** mg versus placebo in regard to H₀
- Step 2: If previous step rejects: test MEDI3506 **CC1** mg versus placebo in regard to H₀

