4.2.8.2 Analysis of blood biomarkers

Analysis of blood eosinophils

Blood eosinophils count will be summarised with descriptive statistics at each visit and change from baseline summarised for each post-baseline visit for the ITT population. Change from baseline in blood eosinophils will be analysed using MMRM as described in Section 4.1.2 for the ITT population. Endpoints will be log transformed prior to analysis. Estimates of the least square mean change from baseline for each treatment, and the difference between them, together with two-sided 80% confidence interval and one-sided p-values, will be obtained from the model for each visit. LS Mean change from baseline and two-sided 80% CI for each visit through Week 24 in blood eosinophils will be presented in figure.

Blood eosinophils count will be also summarised in shift tables comparing maximum value during treatment to baseline value for the ITT population.

Other exploratory biomarkers

The following serum and plasma biomarkers will be collected and summarised:

- Total IgE, allergen-specific IgE, sST2 (serum);
- Plasma EDN;
- CCI
- Serum IL-5;
- Serum IL-13;
- Serum TSLP.

Allergen-specific IgE status and Serum IL33:ST2 at baseline will be used for subgroup analysis of the primary endpoint (pre-BD FEV₁) as described in Section 4.2.4.3. The subgroup cut-off for Serum IL33:ST2 is the Serum IL33:ST2 baseline median.

All the above biomarkers, except allergen specific IgE will be summarised with descriptive statistics at each visit and change from baseline summarised for each post-baseline visit. Change from baseline in all the above biomarkers, except allergen specific IgE and Serum IL33:ST2 will be analysed using a MMRM as described in Section 4.1.2. Endpoints will be log transformed prior to analysis. LS Mean change from baseline and two-sided 80% CI for each analysed visit will be presented in figures.

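### The visible subgroup and biomarker analyses compare treatments within levels but never estimate the between-level difference in effect, which is what the predictive-biomarker objective asks about

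*SAP*

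**What the plan says.** Table 4 in Protocol Section 3 includes an exploratory objective, partly redacted, on "inflammatory blood biomarkers that may predict an efficacy response to MEDI3506". The visible endpoint under it links allergen-specific IgE to the Week 16 efficacy outcomes. Protocol 9.4.3 leaves subgroup methods to the SAP.

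SAP 4.2.4.3 says that for each factor listed in SAP 3.1.7 "a separate MMRM will be fitted using the same covariates as described for the primary analysis", with results shown in a forest plot. Region, ICS dose and background medication each leave the covariate list when they define the subgroup. The model referred to, in SAP 4.1.2, has only two interactions, baseline with visit and treatment with visit. It yields treatment differences with 80% CIs and one-sided p-values.

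For the biomarkers, SAP 4.2.8.2 states: "Allergen-specific IgE status and Serum IL33:ST2 at baseline will be used for subgroup analysis of the primary endpoint". IL33:ST2 is cut at its baseline median. SAP 3.1.7 lists eosinophils, FeNO, total IgE, allergen sensitisation and two T2 definitions as factors, and sets a floor of 20% of participants for a subgroup to be explored.

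In SAP Appendix C, the relevant outputs (for example Tables 14.2.1.5 and 14.2.23.2) are treatment comparisons by subgroup. No title names an interaction or a difference between levels.

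**The concern.** A marker predicts response if the drug-placebo difference is larger at one level of the marker than at another. The quantity of interest is therefore a difference between two treatment effects. The visible plan produces the two effects, each with its own p-value, and stops there.

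The natural reading of such output is that a marker matters when one level is significant and the other is not. That pattern compares two p-values. It can arise easily when the effect is the same in both levels, because each level holds only part of the sample. At stake is whether the exploratory biomarker objective gets an answer with a stated uncertainty or an informal impression from a forest plot.

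**Working it through.** **Inputs, from SAP 1.3 and 4.1.1.** "A sample size of 216 participants (72 participants per treatment group), randomised 1:1:1"; "assuming a difference of 150 mL between placebo and MEDI3506"; "a between-participant SD of 420 mL"; "Hypothesis testing will be performed at the one-sided 10% level". The documents give no biomarker prevalences, so the splits below are assumptions. 50/50 matches a median cut and 20/80 matches the SAP's 20% floor. All figures use a normal approximation for one dose against placebo, with SD 420 mL in every level.

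**The plan's own figure.** SE = 420 × √(2/72) = 70.0 mL. Power = Φ(150/70.0 − 1.2816) = Φ(0.861) = 80.5%. The SAP's statement that the sample size "will provide at least 80% power" is reproduced.

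**Separate models, same true effect of 150 mL in both levels, 50/50 split.**
- Within-level SE = 420 × √(2/36) = 99.0 mL.
- Within-level power = Φ(150/99.0 − 1.2816) = 59.2%.
- The levels contain different participants, so their results are independent. P(exactly one significant) = 2 × 0.592 × 0.408 = 48.3%.
- In one named direction (for example high yes, low no): 0.592 × 0.408 = 24%.

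**Unequal splits.** P(exactly one) = p₁(1 − p₂) + p₂(1 − p₁).
- 30/70: 0.457 × 0.305 + 0.695 × 0.543 = 0.139 + 0.377 = 51.7%.
- 20/80: 0.373 × 0.263 + 0.737 × 0.627 = 0.098 + 0.462 = 56.0%.

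Most of this comes from the larger level being significant alone, which reflects sample size and nothing else.

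**Direct contrast.** SE(difference) = √(SE₁² + SE₂²). Power for a true between-level difference of 150 mL = Φ(150/SE − 1.2816).

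| Split | Within-level SE (mL) | Within-level power | Exactly one level significant | SE of difference (mL) | 80% CI half-width (mL) | Power for 150 mL difference |
|---|---|---|---|---|---|---|
| 50/50 | 99.0 / 99.0 | 59.2% / 59.2% | 48.3% | 140.0 | 179 | 41.7% |
| 30/70 | 127.8 / 83.7 | 45.7% / 69.5% | 51.7% | 152.8 | 196 | 38.2% |
| 20/80 | 156.5 / 78.3 | 37.3% / 73.7% | 56.0% | 175.0 | 224 | 33.6% |

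For 80% power the between-level difference would have to be (1.2816 + 0.8416) × SE, which is about 297, 324 and 372 mL for the three splits.

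**The case against.** - **The answer can be recovered.** A reader might infer that the plan cannot answer the objective at all. The documents do not support that. If models are fitted within levels, the estimates are independent, and anyone can difference them and combine the SEs. This stands. The gap is that the contrast is neither prespecified nor listed for reporting.
- **The wording is ambiguous.** SAP 4.2.4.3 speaks of a model for each factor, which could mean one model per factor with an unstated subgroup term. Dropping a covariate when it defines the subgroup fits either reading. This also stands, and it is a reason to clarify the text.
- **Redactions.** Parts of the objective, the subgroup list and the exploratory analysis of the primary endpoint (SAP 4.2.4.4) are blacked out. An interaction term for a redacted marker cannot be excluded, so the point covers visible analyses only.
- **Consequences.** A reader might infer that Phase III enrichment will rest on these plots. No visible text says so. The objective is exploratory, and the SAP's decision rule covers only the two dose comparisons on the primary endpoint.
- **Chance positives and lost precision.** A reader might add up the many within-level tests and expect several positives by chance. That is a multiplicity matter, which a between-level contrast does not cure, and the 20% floor leaves the number of tests unknown. Nor do the documents support a material loss of precision from fitting separate models.
- **Match to the named biomarkers.** Most of them use fixed cut-offs, so a 50/50 split need not apply. This is fair, and it is why a range is shown. The result does not improve as the split becomes unequal.

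**Conclusion.** The point holds for the visible analyses. The quantity that addresses the predictive-biomarker objective is not specified, and the output that is specified invites an unreliable side-by-side reading. With a common true effect of 150 mL, exactly one of two levels would be significant in about 48% of cases at 50/50 (24% in a given direction), rising to about 52% at 30/70 and 56% at 20/80. These figures rest on the plan's effect and SD, full evaluable numbers, an SD common to all levels and assumed splits. Covariate adjustment in the MMRM could lower the effective SD and change them.

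This is a worthwhile, low-cost improvement to an exploratory analysis. It does not touch the primary analysis or its error control.

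**What to change.** 1. State in SAP 4.2.4.3 whether models are fitted per factor or per level.
2. At least for the biomarker factors (eosinophils, FeNO, total and allergen-specific IgE, T2 status, IL33:ST2), fit one MMRM on the full ITT population. Add subgroup, treatment-by-subgroup and treatment-by-subgroup-by-visit terms.
3. From that model report, for each dose, the Week 16 effect in each level and the between-level difference in effect with its two-sided 80% CI. Add the difference to the tables and the forest plot.
4. Base any statement that a marker predicts response on that difference alone, labelled exploratory and unadjusted for multiplicity.

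The cost is a few sentences in the SAP and modest reprogramming of exploratory tables, with no new data. The estimates will be imprecise: SE about 140 to 175 mL, and 34 to 42% power for a 150 mL interaction at one-sided 10%. They should be presented as estimates with intervals and not as confirmatory tests. An interval that includes zero should not be read as showing that the effect is the same in both levels.

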4.2.4.4 Exploratory analysis of the primary endpoint

The exploratory analysis of the primary analyses will consist of the following.

The primary analysis will be repeated on the ITT population using data from visits up to and including Week 16 by means of the MMRM as described in section 4.1.2, CCI

Additionally, the exploratory analysis of the primary endpoint will consist of repeating the MMRM analysis (see Section 4.1.2) on the ITT population from visits up to and including Week 24.

Graphical representations of the LS Mean change from baseline and the two-sided 80% CI up to and including Week 24 will be provided by treatment group using the ITT population.

The observed values and absolute change from baseline through Week 24 will be summarised by treatment group using the ITT population.

4.2.5 Analysis of secondary endpoints

4.2.5.1 Analysis of lung function parameters measured in clinic

The observed values and changes from baseline in lung function parameters measured in clinic such as pre-BD FEV₁, post-BD FEV₁, FVC, FEV₁/FVC, percent predicted FEV₁, percent predicted FVC, PEF and FEF_{25-75%} will be summarised by treatment group and visit for the ITT population. Observed values and changes from baseline in pre-BD FEV₁ to 4-hours post administration of IP at Day 1 will also be summarised.

The difference in mean change from baseline in post-BD FEV₁ to Weeks 8 and 16 will be estimated using a MMRM, similar to that described for the primary efficacy analysis (Section 4.1.2). The change from baseline through Week 16 will be included in the model. LS Mean change from baseline and two-sided 80% CI through Week 16 in post-BD FEV₁ will be presented in figures.

All lung function parameters measured in clinic will be also reported in listing using the ITT population.

4.2.5.2 Analysis of ACQ-6

Change from baseline to Week 16 in ACQ-6 will be analysed using MMRM (see Section 4.1.2). LS Mean change from baseline and two-sided 80% CI through Week 24 in ACQ-6 score will be presented in figures.

Observed values and absolute change from baseline through Week 16 will be summarised by treatment group using the ITT population.

As a part of exploratory analysis change from baseline through Week 24 in ACQ-6 will also be analysed.

Number and proportion of participants with a decrease in ACQ-6 score of ≥ 0.5 from baseline to Week 16 and number and proportion of participants achieving ACQ-6 well controlled status at Week 16 (as defined in Section 3.4.3) will be summarised and analysed using chi-squared test as described in Section 4.1.4 for the ITT population.

A listing including results from each of the questions and the ACQ-6 score will be produced for the ITT population.

4.2.5.3 Analysis of SGRQ

Change from baseline to Week 16 in SGRQ total and domain scores will be analysed using MMRM (see Section 4.1.2). LS Mean change from baseline and two-sided 80% CI through Week 16 in SGRQ total score will be presented in figures.

Observed values and absolute change from baseline through Week 16 will be summarised.

As a part of exploratory analysis change from baseline through Week 24 in SGRQ total score will also be analysed.

Number and proportion of participants with a decrease in SGRQ total score of ≥ 4 points from baseline to Week 16 (as defined in Section 3.4.4) will be summarised and analysed using chi-squared test as described in Section 4.1.4 for the ITT population.

A listing including results from each of the question and the total SGRQ score will be produced for the ITT population.

4.2.5.4 Analysis of Asthma CompEx

Time to first asthma CompEx event will be analysed using a Cox proportional hazard model, with group, background medication, geographic region and baseline ICS total daily dose as covariates (see Section 4.1.6). All available data from participants through Week 16 will be included. Additionally, the analysis of time to first asthma CompEx event will be repeated using all available data from participants through Week 24 (end of follow-up).

Time to first asthma CompEx will also be displayed in a Kaplan-Meier plot, including all data through to Week 24 (end of follow-up).

The asthma CompEx event rate will be analysed using negative binomial regression, with the log(follow-up time) included as an offset term and treatment group, geographic region, baseline ICS total daily dose as covariates (see Section 4.1.5). The dependent variable will be the number of asthma CompEx events through Week 16. All available data from participants through to Week 16 will be included, irrespective of whether they discontinued study intervention.

Additionally, the analyses of the asthma CompEx event rate will be repeated using all available data from participants through Week 24 (end of follow-up).

Asthma CompEx events will be also reported in listing for the ITT population.

4.2.5.5 Analysis of FeNO

Relative and percent change from baseline through Week 16 in concentration of FeNO will be analysed using a repeated measures analysis of covariance model, similar to that described for the primary efficacy analysis (Section 4.1.2 – reportable results for variables log-normally distributed). Estimates of the least square mean change from baseline for each treatment, and the difference between them, together with two-sided 80% confidence interval and one-sided p-values, will be obtained from the model for each visit. LS Mean percent change from baseline through Week 16 in concentration of FeNO will be presented in figure. Observed concentration of FeNO and relative and percent change from baseline will be descriptively summarised for the ITT population.

As a part of exploratory analysis change from baseline through Week 24 in concentration of FeNO will also be analysed.

FeNO results will be also reported in listing for the ITT population.

